5.0 Study Procedures

After proper informed consent and/or assent have been obtained, all patients will receive a general anesthesia using standard of care. For all patients randomized to receive regional nerve block (Group A & C) a time out before regional anesthesia will be performed stating patient identification and proposed surgical procedure with location of the block to be performed and the medications to be injected.

Patients randomized to receive regional anesthesia will be prepared following standard universal precautions with application of sterile cleaning solution of chlorhexidine (Chloraprep) or alcohol prior to injections.

The site of local anesthetic injection will be identified according to the landmarks defined by their respective anatomical descriptions. The nerve of Arnold block is located at junction of the ear tragus and external 1/3 of ear canal which will be injected using a 30 G needle with 0.5 ml of Bupivacaine 0.25%. na

The Superficial Cervical Plexus located at Erb's Point, posterior border of the sternocleidomastoid muscle and a bisecting horizontal line drawn from the cricoid cartilage at the level of the sixth vertebrae, which is slightly posterior to the external jugular vein, this site will be injected with 3-5ml of bupivacaine 0.25% with 1:200000 of epinephrine. Surgical procedures lasting longer than 4hrs will require a repeat injection with 2.5-3 ml of bupivacaine 0.25% with 1:200000 epinephrine at this latter location after completion of the surgical procedure prior emergence from anesthesia.

Group A: to receive a homolateral (same side) to surgical site or bilateral if surgery involves both ears regional block at the Erb's point and Nerve of Arnold.

The block will be performed prior to surgical incision and may be repeated at Erb's point only with half the initial volume of local anesthetic (1.5 ml -2.5ml) at completion of surgery prior emergence from anesthesia, if the procedure lasted more than 4 hours after the initial block.

Group B: will receive an anti-emetic drug regiment comprising of dexamethasone 150mcg/kg IV (max dose of 10 mg) and ondansetron 150mc/kg IV (max single dose of 4 mg) at any time after induction of anesthesia and as soon as an intravenous line is available. If, at the anesthesiologist's discretion, ondansetron is re-dose at the end of procedure, a max total dose of 8 mg may be given.

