Group C: Will receive both a homolateral or bilateral if surgery involves both ears, a regional block at Erb's point (superficial cervical plexus block) and will receive an anti-emetic drug regiment comprising of dexamethasone 150mcg/kg IV (max dose of 10 mg) and ondansetron 150mc/kg IV (max single dose of 4 mg) at any time after induction of anesthesia and as soon as an intravenous line is available. If, at the anesthesiologist's discretion, ondansetron is re-dose at the end of procedure, a max total dose of 8 mg may be given.

All three groups will receive a standardized general anesthetic regiment, prior to induction the patient *might* require an oral dose of versed 0.5mg/kg as premedication for separation anxiety. Patients will also receive induction of anesthesia either inhalational oxygen in sevoflurane or intravenous induction if subject patient has an IV access, muscle relaxants will be avoided to preserve facial nerve monitoring as required by the surgical approach. Anesthesia will be maintained with oxygen in sevoflurane or desflurane. Prior to emergence of anesthesia and at any point during the procedure, patients may receive IV analgesics (acetaminophen, morphine, fentanyl, ketamine) for postoperative analgesia according to the standard recommended pediatric dosing regiments commonly used at Riley Hospital.

All three groups will receive the standard PACU protocol for pain management and anti-nausea and vomiting intervention. Following patient's recovery starting upon emergence (t_0), all symptoms indicating nausea and/or vomiting and pain will be recorded and every 15min (t_{15}) thereafter in PACU than every 4-6 hrs. while on the inpatient unit for 24 hrs and will be treated as deemed necessary. For pain assessment a FLACC scale and Visual Analogue Scale (VAS) will be used. Complaints of, or signs or symptoms of, nausea, retching and/or vomiting will be documented in the PACU or floor for 24 hours post-operatively. For patients discharged to home prior to the 24 hours, follow up will be done by phone call using the Rhodes INRV to report post-operative nausea and vomiting.

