We will also review patients chart for requests or demands for any pain medications and anti-emetics, documentation of their usage as well as times of discharge from the recovery room to the floor and their discharge from the hospital. For cost comparison and analysis we will look at itemized billing for medical services related to anesthesia, pharmacy use and IV fluid use, antiemetic interventions, medication for pain throughout hospital stay from recovery room to time of discharge from the hospital. For patients that are discharged the same day of their surgery they will be given The Rhodes INRV survey to fill out at home and will be called by phone the following day to collect that information.

A cost analysis between the three study groups taking into account all the items above will be done to compare overall cost of care between the three study groups.

6.0 Reporting of Adverse Events or Unanticipated Problems Involving Risk to Participants or Others

Risk related to the Blocks

Bleeding

Infection at the site

Intravascular local anesthetic injection

Anaphylactic/allergic reaction

Rare spread of local to deeper structures, inadvertent Phrenic nerve blockade (the injection are superficial, subcutaneous with specific landmarks)

Failure of the block to produce pain relief or to prevent nausea and vomiting

Complications related to the surgical procedure including but not limited to:

Facial nerve blockade

Risk of General Anesthesia

All precautions will be taken care of to avoid the above complications by adhering to standard of practice with strict adherence to standard ASA monitoring will be used at all time, observance of the time out procedure and surgical site marking, using universal precautions for sterility and observance of safe injection technique for the regional blocks with intermittent aspiration and injection to avoid intravascular injection and use of live imaging with ultrasound guidance if necessary.

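### Facial nerve blockade is listed only as a surgical complication and facial function is not recorded, although the block is injected at the operated ear in surgery that needs facial nerve monitoring

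*Combined protocol and SAP*

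**What the plan says.** Section 6.0 of the combined protocol and SAP gives a list of risks of the blocks, followed by a separate line, "Complications related to the surgical procedure including but not limited to". The first item after that line is "Facial nerve blockade". The block list contains "Rare spread of local to deeper structures, inadvertent Phrenic nerve blockade" and names no other nerve. A closing sentence then covers everything listed: "All precautions will be taken care of to avoid the above complications by adhering to standard of practice". It goes on to mention time out, sterility, safe injection technique and ultrasound if needed.

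Section 5.0 describes the injections. On the ear injection it says: "The nerve of Arnold block is located at junction of the ear tragus and external 1/3 of ear canal". The second site is Erb's point. Group A is "to receive a homolateral (same side) to surgical site or bilateral if surgery involves both ears regional block", and for that group "The block will be performed prior to surgical incision". The standard anesthetic for all three groups carries a restriction: "muscle relaxants will be avoided to preserve facial nerve monitoring as required by the surgical approach".

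From emergence onward, section 5.0 records nausea, vomiting and pain. Chart and billing review adds medication use, discharge times and cost. Facial movement or function does not appear.

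**The concern.** The block is the intervention under test, so the plan should be able to recognize a harm that the block might cause. In section 6.0 the word blockade, applied to the phrenic nerve, means an effect of local anesthetic and is listed as a block risk. Applied to the facial nerve, the same word appears only among surgical complications. The one facial nerve entry in the adverse event section therefore points away from the block.

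The nerve in question is also the one whose monitoring the plan wants preserved. The plan keeps one class of drug away from that monitoring but does not say how the study's own injections at the operated ear relate to it.

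Two things are at stake. One is the safety of children having surgery for which the plan calls for monitoring. The other is an honest account of the block's harms: facial weakness at emergence in a blocked child could go unrecorded, or be read as surgical because the protocol offers no other explanation.

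**Working it through.** The plan gives no figure on this point. Its only calculation (section 8.0) concerns nausea and vomiting rates and does not enter. The check is mainly a comparison of texts.

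1. **Where the facial nerve entry sits.**

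| Item in section 6.0 | Listed under block risks | Listed under surgical complications |
|---|---|---|
| Spread of local anesthetic to deeper structures | yes | no |
| Phrenic nerve blockade | yes | no |
| Facial nerve blockade | no | yes |

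The general mechanism, spread, is attributed to the block. The facial nerve is not named there.

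2. **Who is exposed, and when.** Section 4.0 plans 20 children per group. Section 5.0 treats Groups A and C as the block groups, so 20 + 20 = 40 of 60 children receive some block. The ear injection before incision is explicit only for Group A (20). The Group C text names only Erb's point and gives no timing, although section 4.0 describes that group as receiving the block plus drugs. Section 2.0 speaks in general terms of a plexus block before surgery. The number receiving an ear injection before incision is therefore 20 on the narrow reading and 40 on the broad one.

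3. **What safeguard is written.** The closing sentence of section 6.0 refers to all the complications above it, and so includes the facial nerve. Its contents are general: aspiration is directed at intravascular injection, and ultrasound is optional. No measure is specific to the facial nerve, and no sentence connects the block with the monitoring.

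4. **What would be observed.** Section 5.0 schedules nausea, vomiting and pain from emergence. No facial observation is planned in any arm, and no rule says how facial weakness would be attributed. The text of sections 8.0 and 11.0 names no safety analysis.

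5. **What a by-arm record could show.** With no events among n children, the one-sided 95% upper limit for the rate is 1 − 0.05^(1/n).
   - n = 40: 1 − 0.05^(1/40) = 0.072, about 7%.
   - n = 20: 1 − 0.05^(1/20) = 0.139, about 14%.

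The record would be descriptive. It could show a frequent problem or document single cases next to the unblocked arm, but it could not exclude a rare one.

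**The case against.** Several stronger readings are tempting, and the documents do not support them.

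- **That the risk is left unguarded.** It is not. The precautions sentence covers facial nerve blockade along with the rest. What stands is that nothing specific to that nerve is written.
- **That the block can defeat the monitoring.** No section says that bupivacaine at these sites can reach the facial nerve or silence the monitor. Section 6.0 calls the injections superficial and subcutaneous, and the ear injection is 0.5 ml. Withholding relaxants and placing a block are not contradictory on the plan's own terms. The possibility is an inference from the ear injection, the acknowledged spread and the plan's own listing of facial nerve blockade.
- **That a case would be coded as surgical.** Section 6.0 is a list of risks, not a coding rule. With randomization and an unblocked arm, a comparison by arm would not depend on attributing each case. That reply is sound, but it needs facial function to be recorded, and it is not.
- **That a case in this trial is likely.** The documents give no rate, and any probability would only reflect the rate assumed. Among 40 children, 1 − (1 − p)^40 is 4% at p = 0.1%, 18% at p = 0.5% and 87% at p = 5%. No such figure should be relied on.
- **That the stopping rule makes matters worse.** Section 7.0 concerns unanticipated events. Facial nerve blockade is a listed risk under either heading, so moving it would not clearly change how the rule works.

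It can also be said that list levels may have been lost when the PDF was read. That leaves slight doubt about the scope of the surgical line, but the facial nerve entry follows it directly.

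**Conclusion.** The point holds in a limited form. Section 6.0 names facial nerve blockade only as a complication of surgery. The plan has no safeguard specific to that nerve and records no facial function, although it injects local anesthetic at the operated ear before incision and wants facial nerve monitoring preserved.

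Its size can be stated only as exposure: 20 children if the ear injection before incision belongs to Group A alone, 40 if Group C receives the same. No event rate or expected count can be given. The conclusion assumes that the extracted list order matches the original. It also assumes that blockade has the same meaning for the facial nerve as for the phrenic nerve in the same section. An effect on monitoring remains an inference. The efficacy comparison is not affected. The weakness is that a possible harm of the tested intervention could be missed or put down to surgery, and it is worth correcting because the correction is cheap.

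**What to change.** 1. In section 6.0, name facial nerve blockade among the block risks. It may also stay under surgical complications.
2. In section 5.0, add a recording of facial function at emergence in all three arms. Report it by arm, with Group B as the no-block comparator, so that attribution does not rest on a heading. Present it as counts with confidence limits rather than as a test, given 20 per arm.
3. Have the investigators reconcile sections 5.0 and 6.0 on the block and the monitoring, and state whether Group C receives the ear injection and when. Any clinical rule on monitoring after the block belongs to the surgical and anesthesia team and is not proposed here.

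The cost is protocol wording and one brief extra observation at a time when children are already assessed for nausea and pain. That observation is new, since facial function is not part of the present assessment.

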7.0 Study Withdrawal/Discontinuation

Subject patient can withdraw from study at their own will and they can do so by letting know the principal investigator or members of the study team. Failure to comply with study protocol may result in withdrawal of patient subject from the study. Should any unanticipated adverse events known to have a direct relation to the procedure occur, the study will be discontinued and IRB will be notified.

8.0 Statistical Considerations

A sample size of 20 subjects per group was selected to provide 80% power for finding a difference between all three groups with nausea/vomiting of 90% vs. 50%, assuming two-sided chi-square tests conducted at a 5% significance level. At completion of study we will submit our data to statistical analysis.

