3.0 Inclusion/Exclusion

Inclusion Criteria

Patient Age 1-18 yo

Scheduled to have cochlear implantation, tympanomastoidectomy, inner ear surgery

Past history of PONV susceptibility

Exclusion Criteria

Patient/ Parents refusal

Infection at the site of local anesthetic injection

Known coagulopathy

Existing VP shunt

Severe mental disability

Any known allergic to dexamethasone (Decadron) and/or ondansetron (Zofran)

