4.0 Enrollment/Randomization

Subject will be approached by [name], the surgeon at his office the day of the preoperative office visit appointment or by any member of the study team the day of the surgery in the preoperative area.

After appropriate assent and consent is obtained subject will be given an identifier and will undergo randomization using a computer program.

Subject will be assigned to either one of the three groups.

Study will involve pediatric patients Age 1-18 years old who are scheduled to undergo inner ear surgery. Subjects will be randomization into three different groups. Each group will consist of 20 patients; we intend to enroll 60 participants total.

Group A Nerve of Arnold block with superficial cervical plexus block (SCPB)

Group B IV dexamethasone (Decadron) + ondansetron (Zofran)

Group C Block + IV dexamethasone (Decadron + ondansetron (Zofran)

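### Allocation and the only named test leave out procedure type; stratifying both on it in two levels guards against chance imbalance at a cost of about 1 point of power

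*Combined protocol and SAP*

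**What the plan says.** All references are to the combined protocol and SAP.

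- **Eligibility (section 3.0).** The surgical criterion is "Scheduled to have cochlear implantation, tympanomastoidectomy, inner ear surgery" and the age criterion is "Patient Age 1-18 yo". No expected mix of procedures is given.
- **Allocation (section 4.0).** After consent the "subject will be given an identifier and will undergo randomization using a computer program". No stratification factor, block scheme or minimisation is mentioned. On numbers: "Each group will consist of 20 patients; we intend to enroll 60 participants total".
- **Sample size (section 8.0).** "A sample size of 20 subjects per group was selected to provide 80% power" for 90% vs 50%, "assuming two-sided chi-square tests conducted at a 5% significance level".
- **Analysis (sections 8.0 and 11.0).** Data will go for statistical analysis once the study is complete. No test, model or covariate is specified for that analysis, so the chi-square test appears only as an assumption behind the sample size.
- **Risk by procedure (section 1.0).** The listed ear operations are described as prone to PONV as a group. No section gives a PONV rate by procedure or by age.

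**The concern.** Type of surgery is on record for every child before allocation, and the eligible operations differ. With arms of 20, chance can easily place noticeably more of one kind of operation in one arm. If that kind carries a different PONV risk, an unadjusted comparison credits or debits the difference to the block or the antiemetics. This is one small trial, and its readers will have to interpret the draw that occurred, not the average over all possible draws. Since no covariate plan exists, any adjustment would also be chosen after the outcomes are available and so be open to selection. Fixing one factor beforehand costs little, and the question is how little.

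**Working it through.** **1. The plan's own figure.** Inputs from section 8.0: p1 = 0.90, p2 = 0.50, two-sided 5%, 80% power. The mean rate is 0.70.

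n = [1.960 × √(2 × 0.70 × 0.30) + 0.842 × √(0.90 × 0.10 + 0.50 × 0.50)]² / 0.40²
= [1.960 × 0.648 + 0.842 × 0.583]² / 0.16 = 19.4, so 20 per group.

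The stated size reproduces as one unadjusted pairwise comparison. Approximate power at 20 per group is 81.3%. Exact enumeration of the uncorrected chi-square gives 83.8%, which is the benchmark below.

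**2. How often imbalance occurs.** Take a two-level factor with prevalence 50% (assumed). With X1 and X2 each Binomial(20, 0.5), X1 + 20 − X2 is Binomial(40, 0.5). Hence P(|X1 − X2| ≥ 5) = 2 × P(Binomial(40, 0.5) ≥ 25) = 0.154. A gap of 5 children is 5/20 = 25 points.

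| Prevalence | Gap ≥5, two given arms | Gap ≥5, at least one of three pairs | Gap ≥6, two given arms |
|---|---|---|---|
| 50% | 15.4% | 32.7% | 8.1% |
| 30% | 11.9% | 26.3% | 5.6% |

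**3. What a bad draw does.** Assumptions: two equal-sized levels, odds ratio (OR) 3 or 6 for PONV between them, 200,000 simulated trials per setting. The null is 70% in both arms, and the alternative is 90% vs 50%. At 70% overall, the level-specific rates are 59% and 81% (OR 3) or 53% and 87% (OR 6).

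For a split of 13/20 vs 7/20, the bias under the null is about (6/20) × (0.81 − 0.59) = 6.6 points, simulated 6.7, or (6/20) × (0.87 − 0.53) = 10.2 points.

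| Given 13 vs 7 | OR 3 | OR 6 |
|---|---|---|
| Chi-square, false positives | 7.1% | 9.6% |
| Mantel-Haenszel, false positives | 4.9% | 5.1% |
| Chi-square, power, adverse split | 72.4% | 64.8% |
| Mantel-Haenszel, power, adverse split | 81.2% | 84.1% |

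Under an adverse split, the unadjusted estimate of the 40-point difference averages 34.6 points (OR 3) or 31.7 points (OR 6).

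**4. Over all draws.** The false-positive rate of the unstratified chi-square under unstratified allocation is 5.3-5.4% whatever the OR.

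**5. Power with one two-level factor, 90% vs 50%, 20 per arm.** The Mantel-Haenszel statistic is (Σ(a − E))² / ΣV over strata, with E = n1·m/N and V = n1·n2·m·(N − m) / (N²(N − 1)), compared with 3.84. Here a is the number of events in arm 1, n1 and n2 are the arm sizes, m the events and N the children in the stratum.

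| Design | OR 1 | OR 3 | OR 6 |
|---|---|---|---|
| Unstratified allocation, chi-square | 83.7% | 83.8% | 83.8% |
| Stratified allocation, chi-square | 83.7% | 84.4% | 85.2% |
| Stratified allocation, two-stratum Mantel-Haenszel | 82.7% | 84.6% | 87.2% |
| Unstratified allocation, two-stratum Mantel-Haenszel | 81.8% | 83.6% | 86.3% |

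The false-positive rate of the Mantel-Haenszel test is 4.8-5.0% in all these settings. Stratified allocation was simulated as an even split within each stratum, to within one child. Real blocks with an unfinished last block come close to this.

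**The case against.** The strongest reply is that randomisation without strata is valid. Step 4 bears this out. A reader might infer from the 7-10% figure that the trial's false-positive rate is inflated. It is not: that figure applies only after a draw as uneven as 13 vs 7, and only if the factor is strongly prognostic. For two given arms, a gap of 6 or more occurs in about 8% of draws.

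The second reply is that the prognostic strength is assumed. This also stands. A reader might take section 1.0 to show that PONV risk differs among the eligible operations, but it ranks them as a group and makes no comparison within it. Section 3.0 also requires past PONV susceptibility, which may narrow the spread of risk. The benefit could therefore be nil.

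The third reply is that no chi-square analysis is actually planned. That is correct. The gap is a missing analysis and covariate plan, not a wrong test laid down in the plan.

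A reader might also infer that adding age, and so using four strata, would be better still. The documents do not support this. They never call age a predictor of PONV, and the age-7 boundary in section 9.0 is an assent rule. A four-stratum test on an unstratified list has 80% power if neither factor matters, 82% if one has OR 3 and 83% if both do, against 84% for the plain test. It gains clearly only if both have OR 6 (87%).

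What remains after these replies is a guard against an unlucky draw on one factor, at a small cost.

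**Conclusion.** The point holds as a recommended, inexpensive improvement; it is not a flaw that invalidates the design. The absence of any stratification or covariate plan, and the 15% and 33% imbalance figures at 50% prevalence (12% and 26% at 30%), are firm. The size of the harm rests on an assumed OR of 3-6 and equal-sized levels. Loss of power under an adverse split (to about 65-72%) is the larger risk, and a spurious positive (about 7-10%) the smaller.

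Stratifying on procedure in two levels changes average power by about −1 point if procedure is irrelevant, and by about +1 to +3 points at OR 3-6. At OR 3 almost all of the gain comes from the allocation (84.4% with the plain test, 84.6% with the stratified one). At OR 6 the matching test adds 2 points. A reader might expect power of up to 90%, but that needs near-deterministic predictors, for example 98% vs 82% within the 90% arm, an odds ratio of about 11. Nothing in the documents supports that.

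Nor can it be said that group sizes will drift from 20: section 4.0 fixes them and simply leaves the method of randomisation unstated. The sample size of 20 is not in error on this point. All power figures are for one pairwise comparison at 5%, with no allowance for making three.

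**What to change.** **Section 4.0.** State that children are allocated 1:1:1 in permuted blocks of varying size, stratified by scheduled procedure in two levels: cochlear implantation vs other.

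**Section 8.0.** Before any outcome is analysed, name for each pairwise comparison the Mantel-Haenszel test stratified by the same two levels, with the stratified risk difference as the estimate. Do not add age as a further stratum.

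**If enrolment has begun.** Leave the allocation as it is and prespecify only the two-stratum procedure test. Its power is 82-86% over OR 1 to 6, a loss of about 2 points if procedure is irrelevant.

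**Cost.** A new randomisation list and a few sentences of SAP text, with no extra children, visits or data. The downside is about 1 point of power if procedure does not predict PONV. Unfinished blocks may leave arms slightly off 20.
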